10.1 Statistical Design	

Predicting Location and Extent of Prostate Cancer using Micro-Ultrasound Imaging

[figure not shown]
10.2	Randomization
10.3	Descriptive Statistics and Exploratory Data Analysis
10.4	Primary Analysis.....
10.4.1	Analysis Population
10.5	Secondary Analysis
10.5.1	Analysis Population
10.6	Sample Size
11.6.1	Accrual estimates
10.7	Criteria for future studies
11.	REFERENCES
12.	APPENDIX A

Predicting Location and Extent of Prostate Cancer using Micro-Ultrasound Imaging

SCHHEMA

This study is to use the ExactVu device, a clinical micro-ultrasound to systematically image the prostate before biopsy or surgery. This is an open, non-randomized, single arm trial. All subjects will know that they will be scanned using the ExactVu device.

SCHEMATIC DIAGRAM

LIST OF ABBREVIATIONS AND DEFINITION OF TERMS (Example)

Include additional abbreviations as needed. Remove any unnecessary abbreviations.

CRF	Case report/Record form
CTCAE	Common Terminology Criteria for Adverse Events
DSMB	Data Safety Monitoring Board
IRB	Institutional Review Board
IV	Intravenous
PD	Progressive diseased
RR	Response rate
SAE	Serious adverse event

1. OBJECTIVES

1.1. Primary Objective

The goal of this study is to use a clinical micro-ultrasound to systematically image the prostate before biopsy or surgery. The images from the ultrasound system will be saved and compared to other imaging modalities and pathology in order to develop better tools for prostate cancer detection using micro-ultrasound. We hope that through the analysis of ultrasound images and comparison to standard of care pathology, we are able to determine the sensitivity of this new platform in our initial cohort.

2. BACKGROUND

2.1. Study Disease

This is an approved clinical ultrasound machine. The goals are to use the device at Stanford for the first time, in correlation with pathology and other imaging modalities. In prior work, our team has developed a database of MRI and pathology data that has been correlated to build predictive models for cancer detection using the MR images. Now, we plan to apply similar methodology using micro-ultrasound instead of MRI. The goal is to improve prostate cancer detection on micro-ultrasound images.

2.2. Study Device – ExactVu is an IDE Exempt Device that will be used according to label

2.3. This study will be register on Clinicaltrials.gov

2.4. Rationale

There are no adequate models for prostate cancer. Since we are hoping to find ultrasound imaging biomarkers that correlate with prostate cancer, human subjects must be used for this project. Because of the established safety of ultrasound, this study is best accomplished on human subjects.

2.5. Preliminary results

2.6. Study Design

- The interventional model:
 - Single Group
- 1 Arm
- The study will not be masked (the party is unaware of the treatment)
 - Open: no masking is used
- The study will not be randomized.

3. PARTICIPANT SELECTION AND ENROLLMENT PROCEDURES

3.1. Inclusion Criteria

3.1.1. Patient scheduled for MR-US fusion prostate biopsy or radical prostatectomy

3.1.2. Ability to understand and the willingness to sign a written informed consent document.

3.2. Exclusion Criteria

3.2.1.1. Does not agree to consent

3.3. Informed Consent Process

All participants will be provided a consent form describing the study with sufficient information for participants to make an informed decision regarding their participation. Participants must sign the IRB approved informed consent prior to participation in any study specific procedure. The participant must receive a copy of the signed and dated consent document. The original signed copy of the consent document must be retained in the medical record or research file.

3.4. Study Completion: This will be a one time imaging scan.

4. IMAGING AGENT/DEVICE/PROCEDURE INFORMATION

4.1. Device/Imaging Procedure: ExactVu

The following diagnostic procedures:

- In the operating room after time-out and anesthesia induction and immediately before radical prostatectomy or in the clinic immediately before biopsy, the EV29L transducer will be inserted in the subject's rectum. Cine sweeps will be performed to save images of:
 1. The entire prostate from posterior to anterior (may require 2 sweeps to cover base and apex)
 2. The peripheral zone using the highest zoom setting (30mm depth) on the system (may require 2 sweeps to cover base and apex).Analysis of these images will be performed after surgery but before prostatectomy or biopsy pathology is available. Reviewers will be blinded to prior biopsy pathology and imaging reports at time of analysis.

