9. MEASUREMENTS/ STATISTICAL CONSIDERATIONS

9.1. Primary outcome will be the prospective data collection of a consecutive series of biopsy and prostatectomy patients.

- PRIMARY OUTCOMES:
 - Evaluate the ability of micro-ultrasound to identify high grade prostate cancer foci (Gleason score ≥ 7) in comparison to final surgical pathology result (prostatectomy or biopsy)

9.2 Secondary outcomes will be an analysis of this data to identify or develop features that form a cancer prediction model

- SECONDARY OUTCOMES:
 - Evaluate the ability of micro-ultrasound to identify the borders of prostate cancer foci in comparison to final surgical pathology result in men after prostatectomy.
 - Evaluate the ability of micro-ultrasound to detect low grade prostate cancer foci (Gleason score 6)
 - Comparison of prostate cancer detection between micro-ultrasound and multiparametric magnetic resonance imaging (mpMRI).
 - Perform a detailed pathologic and imaging correlation between findings on micro-ultrasound, MRI and final surgical histopathology in men who undergo prostatectomy

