10.4.1. Analysis Population

The entire cohort

Predicting Location and Extent of Prostate Cancer using Micro-Ultrasound Imaging

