10.6. Sample Size

Statistical Power for N=68:

Primary outcome: We seek to characterize the sensitivity of micro-ultrasound at detecting significant cancer, especially in comparison to the sensitivity of standard of care multiparametric MRI. With earlier published data with a sensitivity of 90%, we project to

Predicting Location and Extent of Prostate Cancer using Micro-Ultrasound Imaging

detect significant cancer at a sensitivity of 77% by PIRADS 4 and 5 at Stanford. Therefore, we propose a single micro-ultrasound cohort with a sample size of 68 subjected recruited to reach 80% power at alpha level of 0.05.

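### Section 4.1 does not specify that image reviewers are masked to cohort (pre-prostatectomy or pre-biopsy), so pooled sensitivity for Gleason ≥7 cancer can be biased upward by an unknown amount

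*Combined protocol and SAP*

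**What the plan says.** Section 3.1.1 admits two kinds of patient: "Patient scheduled for MR-US fusion prostate biopsy or radical prostatectomy". Section 4.1 has the first kind scanned in the clinic and the second in the operating room, under the same imaging protocol.

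Section 4.1 contains the only rules on how images are read. On timing: "Analysis of these images will be performed after surgery but before prostatectomy or biopsy pathology is available". On masking: "Reviewers will be blinded to prior biopsy pathology and imaging reports at time of analysis". Section 2.6 says of the study as a whole: "Open: no masking is used".

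The primary outcome in section 9.1 is identification of Gleason ≥7 foci, "in comparison to final surgical pathology result (prostatectomy or biopsy"), so both reference standards feed one outcome. Section 10.4.1 gives the primary analysis population as "The entire cohort". Section 10.6 names the quantity of interest: "We seek to characterize the sensitivity of micro-ultrasound at detecting significant cancer". Sections 10.3 to 10.6 plan no analysis by cohort, and no specificity or false-positive measure is named as primary.

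**The concern.** Withholding prior biopsy results keeps a reviewer from knowing that cancer has already been found. The cohort label can return part of that information, because a man about to have his prostate removed can ordinarily be taken to have a cancer diagnosis. The label is not on the list of withheld items.

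A reviewer who believes cancer is present may accept weaker image evidence before marking a lesion. Among prostatectomy patients with Gleason ≥7 cancer, that raises the hit rate. Among prostatectomy patients with Gleason 6 only, who are negative for the primary target, it adds false positives. Sensitivity records the first effect and not the second.

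Section 10.1 says the data are meant to help plan larger, multi-institutional studies. A sensitivity raised in this way would be carried into that planning. A pooled figure reported alone would not show whether the prostatectomy cases were driving it.

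**Working it through.** **1. What reviewers are kept from knowing**

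| Information | Masked? | Source |
|---|---|---|
| Prior biopsy pathology | Yes | 4.1 |
| Imaging reports | Yes | 4.1 |
| Pathology from the current procedure | Yes, by timing of the read | 4.1 |
| Cohort: prostatectomy or biopsy | Not specified | 4.1 silent; 2.6 states no masking |

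The plan does not say who the reviewers are, how saved files are labelled or in what order they are read. The gap is therefore an omission: the plan neither tells reviewers the cohort nor keeps it from them.

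**2. The plan's own figure**

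Section 10.6 gives 68 subjects for 80% power at alpha 0.05, with sensitivities of 90% and 77%. A two-sided one-sample test of a proportion, with p0 = 0.77 and p1 = 0.90, gives

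n = [1.96 × √(0.77 × 0.23) + 0.842 × √(0.90 × 0.10)]² / 0.13² = [0.8248 + 0.2525]² / 0.0169 = 68.7.

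That is 69 rounded up, and power at n = 68 is 79.5%, so the stated 68 is reproduced to within one subject. The planned difference of 90 − 77 = 13 points is a yardstick for any bias. Masking reviewers to cohort would not change this sample size.

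**3. How reader bias would enter the pooled figure**

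Let s be the sensitivity without knowledge of cohort, w the share of Gleason ≥7 cases that come from prostatectomy, and d the rise in hit rate among those cases when the cohort is known. Then

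pooled sensitivity = (1 − w) × s + w × (s + d) = s + w × d,

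so the shift is w × d.

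The documents give neither w nor d. Section 10.7 gives an accrual of 100 without a split by cohort. Both ranges below are assumptions.

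| w | d = 0 | d = 5 points | d = 10 points | d = 20 points |
|---|---|---|---|---|
| 0.3 | 0 | 1.5 | 3.0 | 6.0 |
| 0.5 | 0 | 2.5 | 5.0 | 10.0 |
| 0.7 | 0 | 3.5 | 7.0 | 14.0 |

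Entries are the shift in pooled sensitivity, in points. With a non-zero uplift they run from 0.3 × 5 = 1.5 to 0.7 × 20 = 14. The range spans almost tenfold and depends wholly on the assumed inputs.

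**4. What would make d small**

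The primary outcome concerns foci of Gleason ≥7. The cohort label says nothing about where a focus lies or what grade it has. If a hit required the marked lesion to match the pathology focus in location, knowing the cohort would help only through a lower calling threshold. With a patient-level call, any mark could count and d could be larger. The plan states no matching rule, so neither case can be ruled out.

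**The case against.** The strongest reply is that the documents never say reviewers know the cohort, so a flaw is being read out of silence. That is right as far as it goes. A reader might infer from section 4.1 that reviewers are told the cohort, or that scans are read one at a time soon after each procedure so that the cohort is obvious. Neither is stated. Only the absence of a masking rule can be shown.

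Second, the information that bears most directly on the primary target is already withheld: prior pathology, imaging reports and, by timing, the current pathology. This stands, and it limits the likely effect.

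Third, the biopsy cohort is not a neutral contrast. Those men are scheduled for fusion biopsy, so a reviewer has grounds for suspicion there too. The cohorts may differ only in degree.

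Fourth, a reader might infer that the gap could produce a false win over the 77% figure. The arithmetic looks striking: with 68 cases and a cutoff of 60, the chance of success is 1.5% at a true 77%, but 11.5% if the observed rate is shifted to 82% and 29.1% at 85%. Those figures assume that all 68 subjects have Gleason ≥7 cancer and use a cutoff that the plan does not state (the exact binomial rule with an upper tail of at most 0.025). With 34 positive cases, the corresponding cutoff is 32 and the chances are 0.8%, 4% and 10%. Section 10.1 also calls the study primarily exploratory and disclaims a direct comparison with standard of care, and section 10.4 sets no pass/fail test. A false-success claim is therefore not supported.

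The gap in the masking rule survives all of this, as does the pooling of two cohorts with no separate report.

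**Conclusion.** The point holds as a gap in the plan and a possible bias. Section 4.1 does not specify masking to cohort, nothing elsewhere supplies it, and the primary analysis pools the cohorts. If reviewers learn the cohort, the expected direction is a higher pooled sensitivity for Gleason ≥7 cancer, with extra false positives in prostatectomy patients who have Gleason 6 only. It would be wrong to say that the bias touches only men with the target disease.

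The size is unknown. The illustrative 1.5 to 14 points, against a planned difference of 13, rests on an assumed cohort share and an assumed uplift; with zero uplift the bias is zero. The argument also rests on the inference, not stated in the documents, that a planned prostatectomy implies known cancer. The documents do not show that sensitivity will be inflated, only that the plan leaves this open. The correction is worth making because it is cheap and must be in place before reading begins: a read made with the cohort known cannot be undone.

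**What to change.** In section 4.1, extend the masking rule to say that:

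- saved cine files are coded, with procedure type, room and date removed;
- reviewers are not told the cohort;
- biopsy and prostatectomy scans are read in mixed order where the window before pathology allows.

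The last item is conditional because each read must precede that man's own pathology and the plan gives no accrual rate or pathology turnaround. Coding the files does not depend on that window.

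In section 10.4, report sensitivity for each cohort beside the pooled figure, with a false-positive measure. The table by cohort is useful in any case, since the two cohorts have different reference standards.

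The cost is a small amount of file handling and one extra table. The sample size and patient procedures do not change.

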4.2 Procedure Details for Pre-Biopsy Patients

In subjects undergoing pre-biopsy ExactVu micro-ultrasound imaging of the prostate, the imaging will occur immediately before biopsy. Prior to imaging, risks and benefits will be discussed with patient and informed consent will be obtained. He will be placed in a left lateral decubitus position for imaging. The imaging protocol will be identical to that listed above for the pre-surgery micro-ultrasound imaging. After images are complete, the micro-ultrasound probe will be removed and the prostate biopsy will proceed. Apart from the micro-ultrasound imaging, the biopsy will proceed as normal including administration of a single dose antibiotics, a pre-procedure cleansing enema, imaging with a Hitachi Noblus Ultrasound Unit featuring a 7 mHz probe, peri-prostatic anesthetic block, and biopsy core acquisition.

Predicting Location and Extent of Prostate Cancer using Micro-Ultrasound Imaging

At the close of the procedure, the patient will be reminded of the signs and symptoms of urinary sepsis, urinary retention, and excessive bleeding. These risks are a result of the biopsy and are unchanged by the micro-ultrasound imaging.

5. STUDY PROCEDURES

5.1 Criteria for Removal from Study – participation is voluntary and the patients have the right to withdraw consent or discontinue participation at any time without penalty or loss of benefits to which you are otherwise entitled.

6. STUDY CALENDAR

	Screening	Treatment	Off Study after Treatment
Informed consent	X		
Pre-Op	X		
Imaging Scan: ExactVu		X	
Scheduled for MR-US fusion prostate biopsy or radical prostatectomy		X	X
Adverse event evaluation		X	X

7. ADVERSE EVENTS AND REPORTING PROCEDURES

7.1. Potential Adverse Events

This protocol involves little to no risk to participants. Transrectal ultrasound has a long track record of safety. No contrast material will be administered. There is no radiation exposure.

7.2. Adverse Event Reporting

For guidance on reporting adverse events, refer to the Adverse Event SOP. Please modify the below template language as needed.

Adverse events will be graded according to CTCAE v4.0. Both Serious and Non-Serious Adverse Events will be clearly noted in source documentation and listed on study specific Case Report Forms (CRFs). The Protocol Director (PD) or designee will assess each Adverse Event (AE) to determine whether it is unexpected according to the Informed Consent, Protocol Document, or Investigator's Brochures, and related to the investigation. All Serious Adverse Events (SAEs) will be tracked until resolution and 30 days after the last dose of the study treatment.

8. REGULATORY CONSIDERATIONS

8.1. Institutional Review of Protocol

The protocol, the proposed informed consent and all forms of participant information related to the study (e.g. advertisements used to recruit participants) will be reviewed and approved by the Stanford IRB and Scientific Review Committee (SRC). Any changes made to the protocol will be submitted as a modification and will be approved by the IRB and SRC prior to implementation. The Protocol Director will disseminate the protocol amendment information to all participating investigators.

8.2. Data Management Plan

The study team will develop paper CRF's tracking patient identifiers, prostate cancer history including the most PSA lab value, results of any U/S or MR imaging, results of prior biopsy, results of genomic or other laboratory tests. Date of micro-ultrasound will be stored, along with pathology (either biopsy or prostatectomy final pathology). Data will then be transcribed into OnCore and REDCAP for use of research analysis. All paper CRFs will be stored in a locked filing cabinet and retained until study conclusion. After data is entered into REDCAP, and validated by the research team, each data record will be locked to reduce risk of inadvertent deletion or error. As further described in the Data and Safety Monitoring plan, routine data reviews will occur at 8 week intervals. In future work, data may be transferred or receive to/from collaborators to pool data from various sites. In this case, all data extracted will be de-identified, as per IRB and appropriate data sharing agreements, as applicable.

8.3. Data and Safety Monitoring Plan

During the clinical investigation, the Protocol Director will evaluate the progress of the trial, including periodic assessments of data quality and timeliness, participant recruitment, accrual and retention, participant risk versus benefit, performance of trial sites, and other factors that can affect study outcome. Monitoring of the trial will occur every 8 weeks and a record of monitoring activities will be maintained by the study team. As part of this routine data review, if there are any discrepancies in the data values stored in REDCAP, the research team will manually audit paper CRFs and clinical notes from the EMR will be done to ensure data validity.

The Stanford Cancer Institute Data and Safety Monitoring Committee (DSMC) will audit study related activities at least annually in accordance with the DSMC SOP to determine whether the study has been conducted in accordance with the protocol, local standard operating procedures, FDA regulations, and Good Clinical Practice (GCP). This may include review of regulatory binders, case report forms, eligibility checklists, and source documents. In addition, the DSMC will regularly review serious adverse events and protocol deviations associated with the research to ensure the protection of human subjects. Results of DSMC audits will be communicated to the IRB and the appropriate regulatory authorities at the time of continuing review, or in an expedited fashion, as needed.

9. MEASUREMENTS/ STATISTICAL CONSIDERATIONS

9.1. Primary outcome will be the prospective data collection of a consecutive series of biopsy and prostatectomy patients.

- PRIMARY OUTCOMES:
 - Evaluate the ability of micro-ultrasound to identify high grade prostate cancer foci (Gleason score ≥ 7) in comparison to final surgical pathology result (prostatectomy or biopsy)

9.2 Secondary outcomes will be an analysis of this data to identify or develop features that form a cancer prediction model

- SECONDARY OUTCOMES:
 - Evaluate the ability of micro-ultrasound to identify the borders of prostate cancer foci in comparison to final surgical pathology result in men after prostatectomy.
 - Evaluate the ability of micro-ultrasound to detect low grade prostate cancer foci (Gleason score 6)
 - Comparison of prostate cancer detection between micro-ultrasound and multiparametric magnetic resonance imaging (mpMRI).
 - Perform a detailed pathologic and imaging correlation between findings on micro-ultrasound, MRI and final surgical histopathology in men who undergo prostatectomy

10. STATISTICAL CONSIDERATIONS

10.1. Statistical Design

This study is primarily exploratory, with the goal of collecting the initial correlative data between micro-ultrasound, conventional imaging, and pathology gold standard. As such, we are not intending to directly compare this imaging modality with standard of care, but rather to rigorously and prospectively collect this data in order to plan for larger, multi-institutional studies.

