10.4. Primary Analysis

A prospective collection of correlative data including micro-ultrasound, MR imaging U/S, PSA and pathology data.

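### The primary analysis (10.4) gives no analysis of the Gleason ≥ 7 detection outcome, and 10.1 and 10.6 disagree on whether micro-ultrasound is to be compared with MRI

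*Combined protocol and SAP*

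**What the plan says.** **Primary outcome.** Section 9.1 opens with "Primary outcome will be the prospective data collection of a consecutive series of biopsy and prostatectomy patients". The only bullet below it is "Evaluate the ability of micro-ultrasound to identify high grade prostate cancer foci (Gleason score ≥ 7) in comparison to final surgical pathology result", with prostatectomy or biopsy as the reference. Section 1.1 hopes to determine the sensitivity of the platform in this first cohort.

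**Primary analysis.** The whole of 10.4, apart from the analysis population in 10.4.1 (the entire cohort), is "A prospective collection of correlative data including micro-ultrasound, MR imaging U/S, PSA and pathology data".

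**MRI comparison.** Section 10.1 calls the study primarily exploratory and says "we are not intending to directly compare this imaging modality with standard of care". Section 9.2 lists a comparison of detection between micro-ultrasound and mpMRI among the secondary outcomes. Section 10.6, under the label for the primary outcome, wants the sensitivity of micro-ultrasound "especially in comparison to the sensitivity of standard of care multiparametric MRI". It continues "With earlier published data with a sensitivity of 90%, we project to" and then "detect significant cancer at a sensitivity of 77% by PIRADS 4 and 5 at Stanford", and arrives at 68 men for 80% power at alpha 0.05.

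**The concern.** Two things do not fit together.

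First, the stated primary analysis does not answer the diagnostic question that 9.1 lists as primary. A reader of 10.4 cannot tell what number will be reported for Gleason ≥ 7 detection, in what unit, or with what measure of uncertainty. Those choices could then be made after the reads and the pathology are both available.

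Second, the MRI comparison is disclaimed in 10.1 but appears in 10.6 within the primary outcome, with a power and an alpha attached. Section 10.6 itself calls mpMRI standard of care, so 10.1 cannot be taken to mean some other comparator. A later report could present a micro-ultrasound result set against 77% either as a powered primary finding or as something never intended, and cite the protocol for both.

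This matters because 10.1 says the data are meant to plan larger multi-institutional studies. The estimate carried forward should be defined beforehand.

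**Working it through.** **1. Is the diagnostic outcome analysed anywhere else?** Reading section 10 through:

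| Section | Content | Analysis of Gleason ≥ 7 sensitivity? |
|---|---|---|
| 10.3 | Cohort description and comparison with the usual clinical cohort | No |
| 10.4 | Collection of data | No |
| 10.5 | Co-registration and machine-learning models | No |
| 10.6 | Sample size; sensitivity named, no test or estimator | No |
| 10.8 | Visual feedback and ROC analysis of initial models | No |

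So 1.1, the bullet in 9.1 and 10.6 all point to a diagnostic primary outcome, and no section says how it will be estimated.

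**2. What does the 68 rest on?** Inputs from 10.6: 90%, 77% (PIRADS 4 and 5), power 80%, alpha 0.05. Not given: the test, the number of sides, and the modality to which the 90% belongs.

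One-sample test of a proportion, normal approximation, two-sided, p0 = 0.77, p1 = 0.90:

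n = [(z0.975·√(p0(1−p0)) + z0.80·√(p1(1−p1))) / (p1−p0)]²

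= [(1.960 × 0.4208 + 0.842 × 0.3000) / 0.13]² = (1.0773 / 0.13)² = 68.7

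Power at n = 68: Φ[(0.13 × √68 − 1.960 × 0.4208) / 0.3000] = Φ(0.824) = 79.5%.

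The stated 68 is therefore approximately reproduced (69 if rounded up). Other variants:

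| Variant (two-sided unless stated) | n |
|---|---|
| Normal approximation, one-sided | 53 |
| Normal approximation with continuity correction | 77 |
| Arcsine | 62 |
| Normal approximation, 90% as the null and 77% as the alternative | 53 |
| Two independent groups | 127 per group |
| Paired (McNemar), discordant share 0.15 | 68 |
| Exact binomial, 90% as the null and 77% as the alternative | 68 (power 81.6%) |

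The last two rows also reach 68. The discordant share of 0.15 is an assumption, since the plan gives none. The derivation thus cannot be identified uniquely from the text. What the routes to 68 share is that the PIRADS 4 and 5 figure of 77% is one of the two values set against each other, under a power and an alpha. That is a comparison involving an MRI figure, and it sits badly with 10.1.

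**3. What would estimation alone deliver?** Sensitivity is computed only among men with Gleason ≥ 7 cancer. The plan gives no prevalence, so 40%, 50%, 60% and 100% of 68 are shown as assumptions, with the nearest whole count to 90% detected and exact (Clopper–Pearson) 95% intervals:

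| Men with Gleason ≥ 7 | Detected | Exact 95% CI |
|---|---|---|
| 27 (40%) | 24 | 71% to 98% |
| 34 (50%) | 31 | 76% to 98% |
| 41 (60%) | 37 | 77% to 97% |
| 68 (100%) | 61 | 80% to 96% |

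**The case against.** The strongest reply is that this is an exploratory first-use study, and that 10.1 means only that no confirmatory head-to-head claim will be made. On that reading a descriptive mpMRI comparison in 9.2 is unobjectionable. This part stands: a reader might infer that 10.1 and 9.2 contradict each other, but they are compatible if the comparison is descriptive. The reply does not reach 10.6, which places the comparison under the primary outcome and attaches power and alpha. One could add that a test of a single cohort against a fixed 77% is a benchmark and not a direct comparison. That softens the conflict, but the comparative wording in 10.6 remains, and neither 10.1 nor 10.4 mentions a benchmark test.

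A reader might also infer that the primary endpoint is met simply by enrolling men and filing data, whatever micro-ultrasound detects. The documents do not support that: 1.1, the bullet in 9.1 and 10.6 all name a diagnostic aim. Nor is the absence of a pass mark a fault, since an estimation study need not have one.

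Finally, a reader might take the 13-point gap between 90% and 77% as the size of the problem, or take the 68 as miscalculated. Neither follows. The gap is the difference between two planning values, and the 68 can be reproduced.

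**Conclusion.** The concern holds as an inconsistency in the plan's text. Two points are firm and need no assumption: 10.4 provides no analysis of the diagnostic outcome that 9.1 lists as primary, and 10.1 and 10.6 give the MRI comparison incompatible standing. That the sample size rests on an MRI figure is a reasonable inference from the 77% in 10.6 and the 68.7 obtained above. It remains an inference, because no test is stated.

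The consequence is an undefined primary result and an unsettled status for the MRI comparison. No shift in any estimate can be calculated from this. The interval widths above show what the cohort could support: about 16 percentage points wide if all 68 men have Gleason ≥ 7 cancer, and about 27 if 27 do, at an observed sensitivity near 90%. The change should be made before the reads are compared with pathology.

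**What to change.** - **9.1:** keep detection of Gleason ≥ 7 cancer against pathology as the only primary outcome, and describe prospective collection as the means of obtaining it.
- **10.4:** state the primary analysis as the sensitivity of the blinded micro-ultrasound read (the blinding is already in 4.1) for Gleason ≥ 7, with an exact 95% confidence interval. Name the unit (patient or focus) and the threshold for a positive read; without both, the analysis cannot be run unambiguously. If the unit is the focus, the interval must allow for several foci in one man.
- **10.1:** say that the mpMRI comparison is secondary, descriptive and made within the same men, with no superiority claim.
- **10.6:** remove the comparative phrase and replace the 90%/77% power statement with the expected interval for the anticipated number of men with Gleason ≥ 7 cancer, giving the assumed prevalence. If only the phrase were removed, the power statement would have no hypothesis behind it. The rewrite should also say how the 68 relates to the 100 participants in 10.7.

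The alternative is to keep the test against 77%. Then 10.1 and 10.4 must state it, with its null value, number of sides and test.

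The cost is protocol wording in four places, including a full rewrite of the justification in 10.6, submitted as a modification under 8.1. No additional data are needed. The sponsor gives up a powered claim against MRI, which 10.1 already disclaims.
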